6.3.1 Inclusion Criteria for Subject Selection

All inclusion criteria must be present for the patient to be eligible for enrollment.

Note: the I/E criteria refer to the patient's baseline condition prior to PCI.

General Inclusion Criteria

1. Age ≥ 18 years.
2. Patient with an indication for PCI including angina (stable or unstable), silent ischemia (in absence of symptoms a visually estimated target lesion diameter stenosis of $\geq 70\%$, a positive non-invasive stress test, or FFR ≤ 0.80 must be present), NSTEMI, or recent STEMI. For STEMI the time of presentation to the first treating hospital, whether a transfer facility or the study hospital, must be >24 hours prior to enrollment and enzyme levels (CK-MB or Troponin) demonstrating that either or both enzyme levels have peaked.
3. An attempt (whether successful or not) was made to implant a 38 mm EluNIR stent (Stent was advanced beyond the guiding catheter).

4. Non-target vessel PCI are allowed prior to enrollment depending on the time interval as follows:

a. During Baseline Procedure:

PCI of non-target vessels performed during the baseline procedure itself immediately prior to enrollment if successful and uncomplicated defined as: <50% visually estimated residual diameter stenosis, TIMI Grade 3 flow, no dissection \geq NHLBI type C, no perforation, no persistent ST segment changes, no prolonged chest pain, no TIMI major or BARC type 3 bleeding.

b. Less than 24 hours prior to Baseline Procedure:

Not allowed (see exclusion criteria #2).

c. 24 hours-30 days prior to Baseline Procedure:

- i. PCI of non-target vessels 24 hours to 30 days prior to enrollment if successful and uncomplicated as defined above.
- ii. In addition, in cases where non-target lesion PCI has occurred 24-72 hours prior to the baseline procedure, at least 2 sets of cardiac biomarkers must be drawn at least 6 and 12 hours after the non-target vessel PCI.
- iii. If cardiac biomarkers are initially elevated above the local laboratory upper limit of normal, serial measurements must demonstrate that the biomarkers are falling.

d. Over 30 days prior to Baseline Procedure:

PCI of non-target vessels performed greater than 30 days prior to procedure whether or not successful and uncomplicated.

5. Patient or legal guardian is willing and able to provide informed written consent and comply with follow-up visits and testing schedule.

Angiographic inclusion criteria (visual estimate)

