6.3.2 Exclusion Criteria for Subject Selection

All exclusion criteria must be absent for the patient to be eligible for enrollment.

General Exclusion Criteria

1. STEMI within 24 hours of initial time of presentation to the first treating hospital, whether at a transfer facility or the study hospital or patients in whom enzyme levels (either CK-MB or Troponin) have not peaked.

2. PCI within the 24 hours preceding the baseline procedure.
3. Non-target lesion PCI in the target vessel within 12 months of the baseline procedure.
4. History of stent thrombosis.
5. Cardiogenic shock (defined as persistent hypotension (systolic blood pressure <90 mm/Hg for more than 30 minutes) or requiring pressors or hemodynamic support, including IABP).
6. Subject is intubated.
7. Known LVEF <30%.
8. Relative or absolute contraindication to DAPT for 6 months in non-ACS patients and 12 months in ACS patients (including planned surgeries that cannot be delayed, or on or indicated for chronic oral anticoagulant treatment).
9. eGFR<30 ml/min/1.72 m²
10. Hemoglobin <10 g/dL.
11. Platelet count <100,000 cells/mm³ or >700,000 cells/mm³.
12. White blood cell (WBC) count <3,000 cells/mm³.
13. Clinically significant liver disease.
14. Active peptic ulcer or active bleeding from any site.
15. Bleeding from any site within the prior 8 weeks requiring active medical or surgical attention.
16. If femoral access is planned, significant peripheral arterial disease which precludes safe insertion of a 6F sheath.
17. History of bleeding diathesis or coagulopathy or will refuse blood transfusions.
18. Cerebrovascular accident or transient ischemic attack within the past 6 months, or any permanent neurologic defect attributed to CVA.
19. Known allergy to the study stent components cobalt, nickel, chromium, molybdenum, Carbosil®, PBMA, or limus drugs (ridaforolimus, zotarolimus, tacrolimus, sirolimus, everolimus, or similar drugs or any other analogue or derivative or similar compounds).
20. Known allergy to protocol-required concomitant medications such as aspirin, or DAPT (clopidogrel, prasugrel, ticagrelor), or heparin and bivalirudin, or iodinated contrast that cannot be adequately pre-medicated.
21. Any co-morbid condition that may cause non-compliance with the protocol (e.g. dementia, substance abuse, etc.) or reduced life expectancy to <24 months (e.g. cancer, severe heart failure, severe lung disease).

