		Develops in presence of extracardiac condition that intensifies myocardial ischemia (secondary UA)	Develops in the absence of extracardiac condition (primary UA)	Develops within 2 weeks after acute myocardial infarction (postinfarction UA)
I	New onset of severe angina or accelerated angina; no rest pain ¹	IA	IB	IC
II	Angina at rest within past month but not within preceding 48 hours (angina at rest, subacute)	IIA	IIB	IIC
III	Angina at rest within 48 hours (angina at rest, acute)	IIIA	IIIB	IIIC

¹ Subjects with new onset (< 2 months in duration) exertional angina pectoris that is severe or frequent (>3 episodes/day) or subjects with chronic stable angina who develop accelerated angina (that is, angina distinctly more frequent, severe, longer in duration, or precipitated by distinctly less exertion than previously) but who have not experienced pain at rest during the preceding 2 months.

BLEEDING (HEMORRHAGIC) COMPLICATIONS

Bleeding will be classified and reported by both the TIMI bleeding classification and the BARC classification.

TIMI Bleeding Classification

Major:	Intracranial or clinically significant overt signs of hemorrhage associated with a hemoglobin decrease greater than 5g/L*. The diagnosis of intracranial bleeding requires confirmation by computed tomography or magnetic resonance imaging of the head.
Minor:	Observed blood loss and a decrease in hemoglobin level of 3 to 5 g/dL*

Bleeding Academic Research Consortium (BARC) Classification:

Type 0	No bleeding
Type 1	Bleeding that is not actionable and does not cause the patient to seek unscheduled performance of studies, hospitalization, or treatment by a health care professional. May include episodes leading to self-discontinuation of medical therapy by the patient, without consulting a health care professional.
Type 2	Any overt, actionable sign of hemorrhage (e.g. more bleeding than would be expected for a clinical circumstance; including bleeding found by imaging alone) that does not fit the criteria for Types 3, 4, or 5 but does meet at least one of the following criteria: 
• Requiring non-surgical, medical intervention by a health care professional• Leading to hospitalization of increased level of care• Prompting evaluation
Type 3a	
• Overt bleeding plus hemoglobin drop of 3 to <5** g/dL (provided hemoglobin drop is related to bleed)• Any transfusion with overt bleeding

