Type 3b	
• Overt bleeding plus hemoglobin drop \geq5** g/dL (provided hemoglobin drop is related to bleed)• Cardiac tamponade• Bleeding requiring surgical intervention for control (excluding dental / nasal / skin / hemorrhoid)• Bleeding requiring intravenous vasoactive agents
Type 3c	
• Intracranial hemorrhage (does not include microbleeds or hemorrhagic transformation; does include intraspinal)
◦ Subcategories: confirmed by autopsy or imaging or LP• Intra-ocular bleed compromising vision
Type 4	CABG-related bleeding 
• Perioperative intracranial bleeding within 48 hours• Reoperation following closure of sternotomy for the purpose of controlling bleeding• Transfusion of \geq 5 units of whole blood or packed red blood cells within 48 hour period*• Chest tube output \geq 2 L within a 24 hour period
Type 5a	Probable fatal bleeding; no autopsy or imaging confirmation, but clinically suspicious
Type 5b	Definite fatal bleeding: overt bleeding or autopsy or imaging confirmation

Obs: Platelet transfusions should be recorded and reported, but are not included in these definitions until further information is obtained about the relationship to outcomes.

* Cell saver products will not be counted.

** Corrected for transfusion (1 unit PRBC or 1 unit of whole blood = 1 g/dL Hgb)

CEREBROVASCULAR ACCIDENT (CVA) (See STROKE)

- Ischemic stroke (cerebral infarction); or
- Hemorrhagic stroke (intracerebral hemorrhage or subarachnoid hemorrhage).

CORONARY ARTERY BYPASS GRAFT SURGERY (CABG)

Acute CABG is defined as immediate transfer from the cath lab to the operative room for emergent bypass surgery during the initial treatment phase.

CABG during follow-up is only considered as a clinical-indicated Target Lesion Revascularization if coronary angiography indicates a diameter of stenosis greater than 50% of the stented coronary segment associated with one of the following conditions:

- A positive history of recurrent angina pectoris presumably related to the target vessel.
- Objective signs of ischemia (exercise test or equivalent) presumably related to the target vessel.
- Abnormal results of any invasive functional diagnostic test (e.g. Doppler flow velocity reserve, fractional flow reserve).

DEATH (per ARC definition, Circulation 2007;115:2344-51)

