	Cells/ mm^3	$\times 0.001 = 10^3/\mu\text{L}$
Hemoglobin (g/dL)	g/L	$\times 0.1 = \text{g/dL}$
	mmol/L	$\times 1.611 = \text{g/dL}$
Hematocrit (%)	L/L	$\times 100 = \%$
Serum Creatinine (mg/dL)	$\mu\text{mol/L}$	$\times 0.01131 = \text{mg/dL}$
BUN (mg/dL)	mmol/L	$\times 2.8 = \text{mg/dL}$
Total Cholesterol (mg/dL)	mmol/l	$\times 38.66 = \text{mg/dL}$
LDL (mg/dL)	mmol/l	$\times 38.66 = \text{mg/dL}$
HDL (mg/dL)	mmol/l	$\times 38.66 = \text{mg/dL}$
Triglycerides (mg/dL)	mmol/l	$\times 88.5 = \text{mg/dL}$

If instead of BUN, urea is collected by a site, urea will be converted into BUN and the conversion will be performed as follows:

$$\text{BUN (mg/dL)} = \text{Urea (mg/dL)} / 2.14$$

$$\text{BUN (mg/dL)} = \text{Urea (mmol/L)} * 2.8$$

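### The TIMI major and minor bleeding rows in Protocol 19.1 use different hemoglobin units, so the major cut lies below the minor band and the two grades overlap

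*Protocol*

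**What the plan says.** The bleeding entry in Protocol section 19.1 opens with a commitment: "Bleeding will be classified and reported by both the TIMI bleeding classification and the BARC classification". The TIMI table follows.

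- **Major:** intracranial bleeding, or clinically significant overt hemorrhage with a "hemoglobin decrease greater than 5g/L".
- **Minor:** "Observed blood loss and a decrease in hemoglobin level of 3 to 5 g/dL".

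The BARC table in the same entry works in g/dL. Type 3a covers overt bleeding with a fall of 3 to less than 5 g/dL, and type 3b a fall of 5 g/dL or more. Exclusion criterion 10 (section 6.3.2) is also in g/dL: "Hemoglobin <10 g/dL".

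TIMI major is used outside the glossary. Inclusion criterion 4a (synopsis and section 6.3.1) accepts non-target vessel PCI in the same session only if, among other conditions, there was "no TIMI major or BARC type 3 bleeding". Criterion 4c.i applies the same definition to PCI from 24 hours to 30 days earlier, and section 6.4.2 repeats it. Section 14.9, on adjudication of clinical endpoints, refers to section 19.1 for definitions.

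**The concern.** A severity scale should place each bleed in one grade, with the higher grade starting where the lower one ends. Here the major threshold is in g/L and the minor band in g/dL, and the major threshold falls below the floor of the minor band. Two people grading the same bleed could then disagree while each acts reasonably: one follows the printed unit, the other assumes g/dL was meant. The protocol gives no citation for the TIMI classification that would override the printed value, and section 6.1.3 makes section 19.1 the place where terms are defined.

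At stake are the consistency of the promised TIMI grades and, through the non-target PCI criterion, who counts as eligible.

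**Working it through.** **Inputs**

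- TIMI major: fall > 5 g/L (Protocol 19.1).
- TIMI minor: fall of 3 to 5 g/dL (Protocol 19.1).
- BARC 3a: fall of 3 to < 5 g/dL; BARC 3b: fall ≥ 5 g/dL (Protocol 19.1).
- Conversion: g/L × 0.1 = g/dL (SAP 5.6.3, table of laboratory conversions).

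**Step 1. Common unit.** 5 g/L × 0.1 = 0.5 g/dL. This is one tenth of the top of the minor band (0.5 / 5 = 0.1) and lies below its 3 g/dL floor.

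**Step 2. Grade the same bleed both ways.** Take a clinically significant overt bleed that is not intracranial. The third column reads the major row in the unit of the minor row.

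| Hemoglobin fall (g/dL) | TIMI as printed (major > 0.5) | TIMI if both rows are in g/dL (major > 5) | BARC on hemoglobin alone |
|---|---|---|---|
| 0.5 or less | none | none | not type 3 |
| above 0.5, below 3 | major | none | not type 3 |
| 3 to below 5 | major and minor | minor | 3a |
| exactly 5 | major and minor | minor | 3b |
| above 5 | major | major | 3b |

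As printed, the minor grade alone is left only for blood loss with a fall of 3 to 5 g/dL that is observed but not clinically significant and overt. With one unit, the TIMI bands meet without overlap. They also line up with BARC 3a and 3b, except that a fall of exactly 5 g/dL is TIMI minor but BARC 3b.

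**Step 3. Added effect on eligibility.** The criterion fails on TIMI major or BARC type 3. Overt bleeding with a fall of 3 g/dL or more is already BARC 3, so the printed unit changes nothing there. It can matter only for clinically significant overt bleeds with a fall above 0.5 and below 3 g/dL that are not BARC 3 for another reason, such as transfusion or tamponade. In that range the printed unit makes the criterion stricter.

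**Step 4. Effect on the analysis.** TIMI grades do not enter the primary endpoint (Protocol 6.1.3.1) or the listed secondary endpoints (6.1.3.2). SAP 5.6.1 summarizes adverse events by MedDRA term and intensity, and SAP Appendix 2 lists no bleeding table. The sample size statement also stands apart: 1 − 0.2^(1/50) = 3.17%, and 1 − (1 − 0.032)^50 = 0.803, which reproduces the stated 80% at 3.2% with n = 50.

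**The case against.** The strongest reply is that this is a one-character slip in a glossary with little practical reach. Much of that stands.

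- **Eligibility.** Exclusion 14 removes active bleeding from any site. Exclusion 15 removes bleeding in the prior 8 weeks that needed active medical or surgical attention, whatever the hemoglobin fall. With BARC type 3, these leave few bleeds that only the printed TIMI cut would catch. The data schedule has a pre-procedure blood count and no post-procedure one, so a small fall between two lesions treated in one session would rarely be measured.
- **Committees.** Under section 14.9.5 the CEC adjudicates bleeding that is a serious adverse event or needs transfusion or surgery, so a minor non-serious bleed would not reach it. The data safety monitoring board receives all adverse events, but no TIMI grading is mentioned there, and there are no stopping rules.

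Three stronger readings may tempt a reader, and the documents do not support them.

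- *Trivial bleeds would disqualify patients.* The major row requires clinically significant overt hemorrhage, so a trivial bleed does not qualify at any hemoglobin fall.
- *Every overt bleed with a fall between 0.5 and 5 g/dL is over-graded.* The same qualifier excludes overt bleeds that are not clinically significant.
- *Major bleeding would be inflated in the safety report.* No listed table or specified output reports TIMI grades.

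What does not stand is the view that nothing needs fixing. The protocol commits to TIMI grading and uses TIMI major in an inclusion criterion, and no other passage repairs the unit.

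**Conclusion.** The TIMI table is wrong as written. The major threshold is 0.5 g/dL against a minor band of 3 to 5 g/dL. Clinically significant overt bleeds with falls above 0.5 and below 3 g/dL are graded major without reaching the minor band, and those with falls of 3 to 5 g/dL meet both grades. The wording of the inclusion criterion is not itself misprinted; it inherits the faulty definition.

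The consequence is small. It touches the promised TIMI grades and a narrow band of eligibility decisions. The endpoint definitions, the sample size and the listed SAP tables are unaffected. An indirect route remains: an eligibility failure is a listed major deviation and can remove a subject from the per-protocol set, where one subject in 50 is 2%. The documents give no figure for how often a bleed in the affected range would occur.

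Two assumptions underlie this. The g/L unit must be what the sponsor's source file shows; g/dL appears correctly in the adjacent row, so a reading error is unlikely, but it is quick to check. The judgment that exclusions 14 and 15 absorb much of the remaining eligibility effect comes from their wording, not from data.

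**What to change.** Reconcile the two TIMI rows in section 19.1 to one hemoglobin unit, so that the major and minor bands are contiguous and do not overlap. The minor row, the BARC rows and the hemoglobin exclusion all use g/dL. State which grade a fall of exactly 5 g/dL takes, since TIMI minor and BARC 3b both include it when the bands are aligned. Have the CEC classification rules (section 8.4.1) use the amended table. The inclusion criterion and section 6.4.2 need no rewording, because they take the definition from section 19.1.

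The cost is one unit correction in the protocol. No analysis, endpoint or sample size changes.

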6.1.4.2 Pre-Procedure Laboratory Assessments

The following laboratory assessments are to be performed (having been done as part of routine clinical care) prior to the baseline procedure.

Within 30 days prior to procedure:

- Complete Blood Cell Count (CBC)
- Creatinine, BUN
- Lipid profile (total cholesterol, LDL, HDL, triglycerides)

Within 24 hours pre-procedure:

- Electrocardiogram (ECG)
- Creatine kinase (CK) and creatine kinase muscle-brain isoenzyme (CK-MB) (For subjects with ACS, enzyme levels need to be within 8 hours of the procedure or have already been shown to be decreasing.)
- Troponin (T or I) where CK-MB is not available

Note: If any of the baseline tests were not obtained prior to the PCI procedure they may be obtained (including baseline biomarkers) as soon as possible after enrollment.

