- Class I: Focal ISR group. Lesions are ≤ 10 mm in length and are positioned at the unscuffed segment (i.e., articulation or gap), the body of the stent, the proximal or distal margin (but not both), or a combination of these sites (multifocal ISR);
- Class II: "Diffuse intra-stent" ISR. Lesions are >10 mm in length and are confined to the stent(s), without extending outside the margins of the stent(s).
- Class III: "Diffuse proliferative" ISR. Lesions are >10 mm in length and extend beyond the margin(s) of the stent(s).
- Class IV: ISR with "total occlusion." Lesions have a TIMI flow grade of 0.

MAJOR EPICARDIAL VESSELS

- Left anterior descending artery (LAD) with septal and diagonal branches;
- Left circumflex artery (LCX) with obtuse marginal and/or ramus intermedius branches;
- Right coronary artery (RCA) and any of its branches.

MAJOR ADVERSE CARDIAC EVENTS (MACE)

The composite rate of cardiac death, any MI or ischemia-driven TLR

MINIMUM LUMEN DIAMETER (MLD)

MLD is defined the average of two orthogonal views (when possible) of the narrowest point within the area of assessment – in lesion, in stent or in segment. MLD is visually estimated during angiography by the Investigator; it is measured during QCA by the Angiographic Core Laboratory.

MYOCARDIAL INFARCTION (MI)

Post-PCI (Type 4a) and post-CABG (Periprocedural) MIs (Type 5):

Periprocedural MIs will be defined based on the SCAI definitions (14) as follows:

- 1) In patients with normal baseline CK-MB: The peak CK-MB measured within 48 hours of the procedure rises to ≥ 10 x the local laboratory ULN, or to ≥ 5 x ULN with new pathologic Q-waves in ≥ 2 contiguous leads or new persistent LBBB, *OR* in the absence of CK-MB measurements and a normal baseline cTn, a cTn (I or T) level measured within 48 hours of the PCI rises to ≥ 70 x the local laboratory ULN, or ≥ 35 x ULN with new pathologic Q-waves in ≥ 2 contiguous leads or new persistent LBBB.
- 2) In patients with elevated baseline CK-MB (or cTn) in whom the biomarker levels are stable or falling: The CK-MB (or cTn) rises by an absolute increment equal to those levels recommended above from the most recent pre-procedure level.

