PERCUTANEOUS CORONARY INTERVENTION (PCI)

Refers to all interventional cardiology methods for treatment of coronary artery disease.

PERFORATION

Perforations will be classified as follows:

- Angiographic perforation: perforation detected by the clinical site or the core laboratory at any point during the procedure.
- Clinical perforation: perforation requiring additional treatment (including efforts to seal the perforation or pericardial drainage), or resulting in significant pericardial effusion, abrupt closure, myocardial infarction, or death.
- Pericardial hemorrhage/tamponade: perforation resulting in cardiac tamponade.

PERSISTING DISSECTION

Dissection at follow-up that was present post baseline procedure.

PRIMARY INVESTIGATOR

The physician responsible for conducting the clinical trial at each investigational site.

PRINCIPAL INVESTIGATOR

A physician-specialist, related to the trial, who is responsible for the overall conduct of the trial at all sites and compliance with clinical investigation plan and relevant regulations.

PROTOCOL DEVIATIONS - MAJOR

Major protocol deviations include, but are not limited to, enrollment of a subject:

- Whose informed consent was not properly obtained
- Who did not meet all of the inclusion or exclusion criteria
- Who did not receive at least 6 months of DAPT post baseline procedure

REFERENCE VESSEL DIAMETER (RVD)

Average diameter of proximal and distal healthy segments by QCA. 10 mm “normal” reference segments are selected proximal and distal to the stenosis and averaged to define the reference vessel diameter. A computer-defined interpolated normal segment will be used to calculate percent diameter stenosis.

RESTENOSIS

Re-narrowing of the artery following the removal or reduction of a previous narrowing.

REVASCULARIZATION (per ARC definition, Circulation 2007;115:2344-51)

Target Lesion Revascularization (TLR)

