2.2 Secondary Endpoints

Acute Success evaluated at the time of the baseline procedure by the Angiographic Core Laboratory:

- Device success

Device success is defined as achievement of a final in-stent residual diameter stenosis of <30% (by QCA), using the assigned device only and without a device malfunction.

- Lesion success

Lesion success is defined as achievement of a final in-stent residual diameter stenosis of <30% (by QCA) using any percutaneous method.

- Procedure success

Procedure success is defined as achievement of a final in-stent diameter stenosis of <30% (by QCA) using the assigned device and/or with any adjunctive devices, without the occurrence of cardiac death, Q wave or non-Q wave MI, or repeat revascularization of the target lesion during the hospital stay.

Secondary Clinical Endpoints evaluated at 30 days, 6 months, and 1 year:

All 30-day, 6-month and 1-year clinical events will be adjudicated and classified by an independent Clinical Events Committee (CEC). Only secondary clinical endpoints evaluated at 30 days will be included in the primary analysis and the CSR.

Myocardial infarction (MI) events will be classified as in Table 1 and adjudicated per the Universal Definition of Myocardial Infarction except for Type 4a (post-PCI) and Type 5 (post-CABG) which will be adjudicated based on the SCAI definitions, as follows:

- 1) In patients with normal baseline CK-MB: The peak CK-MB measured within 48 hours of the procedure rises to ≥ 10 times the local laboratory ULN, or to ≥ 5 times ULN with new pathologic Q-waves in ≥ 2 contiguous leads or new persistent LBBB, OR in the absence of CK-MB measurements and a normal baseline cTn, a cTn (I or T) level

 Cardiovascular Research Foundation	FORM	Document N° BIO-TMP-0702 Revision: 00
	TITLE SAP Template	Effective date: 16-Mar-2018 Department: BIO

measured within 48 hours of the PCI rises to $\geq 70x$ the local laboratory ULN, or $\geq 35x$ ULN with new pathologic Q-waves in ≥ 2 contiguous leads or new persistent LBBB.

- 2) In patients with elevated baseline CK-MB (or cTn) in whom the biomarker levels are stable or falling: The CK-MB (or cTn) rises by an absolute increment equal to those levels recommended above from the most recent pre-procedure level.

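### The troponin branch of the periprocedural MI rule counts 48 hours from the PCI even for post-CABG infarcts, so a troponin drawn later than that does not qualify where CK-MB could

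*Protocol*

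**What the plan says.** Protocol 19.1, under myocardial infarction, places two MI types under one heading: "Post-PCI (Type 4a) and post-CABG (Periprocedural) MIs (Type 5". Rule 1 covers subjects with a normal baseline and has two branches.

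- **CK-MB:** "The peak CK-MB measured within 48 hours of the procedure rises to" at least 10 times ULN, or 5 times with new Q waves or persistent LBBB.
- **Troponin, when CK-MB was not measured:** "a cTn (I or T) level measured within 48 hours of the PCI rises to" at least 70 times ULN, or 35 times with the same ECG findings.

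SAP 2.2 repeats the troponin wording ("measured within 48 hours of the PCI rises to"). It takes Types 4a and 5 out of the Universal Definition: "Type 5 (post-CABG) which will be adjudicated based on the SCAI definitions".

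Protocol 19.1 defines PCI as follows: "Refers to all interventional cardiology methods for treatment of coronary artery disease". Bypass surgery has its own entry.

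Troponin alone is an accepted marker. Protocol 6.1.4.2 lists "Troponin (T or I) where CK-MB is not available" for baseline laboratory work. For events after discharge the relevant text is protocol 6.1.4.7, which accepts either CK-MB or troponin when an ischemic event is suspected.

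**The concern.** The two branches are meant to be alternatives for the same event, but they start the clock at different places. For Type 4a the places coincide. For Type 5 they do not: the procedure can be read as the bypass operation, while the PCI cannot, given the protocol's own definition of that term.

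Whether a post-CABG infarct counts can then depend on which assay the hospital runs. Any MI is a component of 30-day MACE, and so of the primary endpoint. MI and target-vessel MI are also separate endpoints at 30 days, 6 months and 1 year, and target-vessel MI enters TLF and TVF. The plan foresees the situation: protocol 14.6 lists CABG, emergent or not, as a foreseeable event, and 6.1.4.5 and 6.1.4.6 collect it at each follow-up.

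**Working it through.** **Plan's own figure.** The only design figure is the 80% chance of seeing at least one event at 3.2% incidence with n = 50 (protocol 7.1). It reproduces: 1 − (1 − 0.032)^50 = 0.803. It does not depend on the MI definition, so nothing below alters the sample size.

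**Step 1: the two windows.** Put the PCI at hour 0 and the CABG at hour c. Read literally, for a Type 5 event:

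- CK-MB window: c to c + 48 hours.
- Troponin window: 0 to 48 hours.

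| Time of CABG | CK-MB window | Post-surgery troponin that counts |
|---|---|---|
| Acute, c near 0 | about 0 to 48 h | nearly all of the same window |
| c between 0 and 48 h | c to c + 48 h | only values drawn by hour 48 |
| c above 48 h, e.g. day 10 (c = 240) | 240 to 288 h | none |

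In the last row no troponin level qualifies, whatever its size, while a CK-MB of 10 times ULN does. Because c is never negative, the literal troponin window never ends later than the CK-MB window. The mismatch can therefore remove events but not add them.

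**Step 2: does another rule catch the case?** Rules 2 and 3 apply to raised baseline markers. They state no window of their own, so those subjects are unaffected, but they do not cover a normal baseline. The SAP removes Type 5 from the Universal Definition. Protocol 14.9.2 has the CEC decide whether each MI is spontaneous or procedure-related, so a bypass infarct should not be recovered as a spontaneous one.

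**Step 3: overlap with other components.** Under protocol 19.1, bypass of the target vessel for a target-lesion complication is TLR. If ischemia-driven, it already counts in MACE and TLF. Bypass of any segment of the target vessel is TVR and, if ischemia-driven, counts in TVF. The standalone MI and target-vessel MI endpoints have no such overlap.

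**Step 4: size on the primary endpoint.** One reclassified subject is 1/50 = 2 percentage points. Exact 95% intervals:

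- 50/50 = 100% (92.9 to 100) becomes 49/50 = 98.0% (89.4 to 99.9).
- 48/50 = 96.0% (86.3 to 99.5) becomes 47/50 = 94.0% (83.5 to 98.7).

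**Step 5: how often.** The documents give no CABG rate. For an assumed 30-day rate r, the chance of at least one CABG among 50 subjects is 1 − (1 − r)^50:

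| Assumed r | Chance of at least one CABG |
|---|---|
| 0.1% | 4.9% |
| 0.5% | 22.2% |
| 1% | 39.5% |
| 2% | 63.6% |

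These are upper limits on the chance of a changed primary result under each assumption. A change also needs an infarct, troponin drawn past hour 48, no CK-MB, a normal baseline, no ischemia-driven TLR, no other MACE component and device success.

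**The case against.** The strongest reply is that adjudication will settle this. The CEC sets explicit rules at the start (protocol 8.4.1), the heading names post-CABG MI, and the neighbouring branch speaks of the procedure. A sensible committee would read the PCI as whichever operation is in question. That is likely, but it would be an undocumented departure from the written definition of a primary-endpoint component, and the SAP repeats the same words.

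A second reply is that the 3rd Universal Definition is a planned sensitivity analysis. It is, but protocol 7.2.2 and SAP 5.2.2 apply it to 30-day MACE only. It leaves the primary analysis and the 6-month and 1-year endpoints as they are. The other two sensitivity definitions change CK-MB thresholds only.

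Third, the trial is descriptive, with no hypothesis test or performance threshold, so a 2-point shift overturns no decision. This stands, and it is why the point is minor.

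A reader might infer that a bypass infarct measured by troponin alone can never qualify when the baseline is normal. The documents do not support that. They provide for early surgery: "Acute CABG is defined as immediate transfer from the cath lab to the operative room for emergent bypass surgery during the initial treatment phase". Troponin drawn after such an operation can fall within 48 hours of the PCI and meet the threshold.

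**Conclusion.** The mismatch is real and is in both documents. With a normal baseline and no CK-MB, a post-CABG infarct does not qualify as MI under the literal rule when the troponin is drawn more than 48 hours after the PCI.

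The consequence is rare and small. In practice the primary endpoint changes only for a CABG between 48 hours and day 30 in a subject with no other failure, at 2 points per subject. A CABG shortly before hour 48 is affected only if no threshold-level troponin is drawn before the window closes.

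A reader might also infer a material bias in the primary result by treating every subject who has a CABG as exposed. The documents give no CABG rate to support this. Timing, assay, baseline level and overlap with TLR each reduce the number further. The clearest effect is on the MI and target-vessel MI rates, where nothing else captures the event. Severity: minor.

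**What to change.** In the troponin branch of rule 1, in protocol 19.1 and SAP 2.2, replace *the PCI* with *the procedure (PCI or CABG)*, so that both markers use the same anchor for Type 4a and Type 5. Do this before adjudication, and carry the wording into the CEC's rules.

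The cost is a few words in each document. No new data are needed and the sample size is unchanged. The only downside is that the event count may be slightly less favourable.
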